7.7 Interim Analysis

7.7.1 Futility Interim Analysis

When data are available from approximately 34 biomarker positive participants and approximately 17 biomarker negative participants, an interim analysis will be performed. An intervention will be stopped for futility if the futility boundary is crossed for both primary endpoints in biomarker positive participants and in the combined group of biomarker positive and negative participants. The probability to declare futility if at least one of the two endpoints has the true effect size of 0.3 (the effect size is defined as the treatment effect divided by the standard deviation of the outcome) in the biomarker positive subgroup is at most 0.16. To test for futility, we compute the test of a treatment effect for FEV₁ percent predicted, and ACQ-6. Larger values of the test statistics correspond to more favorable treatment responses. Futility is declared for an endpoint if test statistics for biomarker positives and for the combined sample of biomarker positives and negatives, are both less than 1.29. The intervention must show futility on both endpoints in both samples (biomarker positives and the combined biomarker positive and negative group) to be dropped from the study. Assuming mutual independence of the outcomes, the probability to stop for futility is 0.74 if there is no effect on any of the two endpoints.

Futility is also tested on the biomarker negative sample alone. Enrollment of biomarker negative participants to the intervention is stopped if futility is established. The cutoff for futility in this analysis is 1.08. If the biomarker negative group is stopped for futility, 77 more biomarker positive participants are enrolled. The above sample size is for interventions with a proportion of biomarker positives among all enrolled to the intervention of 67%, assuming the interim analysis is performed at the 0.45 information fraction and a 10% active treatment discontinuation rate is observed. Adjustments might be made if these parameters are different from the above.

7.7.2 Blinded Sample Size Re-Estimation

The pre-specified blinded interim analysis to estimate the crossover correlation coefficient was conducted, and changes were made to the protocol, as described in Section 1.3 above.

7.7.3 Precision Medicine Interim Analysis

Each of the interventions selected for investigation in PrecISE is hypothesized to work in a specific patient subgroup defined based on one or more predictive biomarkers, and the intervention's effect on patients outside the subgroup is suspected to be smaller. The biomarker positive subgroup is specified as a function of the primary predictive biomarker for that intervention before the first unblinded analysis (futility analysis or the final analysis for interventions where futility analysis is not feasible). A precision medicine interim analysis was originally planned to revise the subgroup definitions for any intervention not stopped for futility by evaluating alternate cut-points delineating biomarker -positive

and negative patients as well as determining whether pre-specified secondary biomarkers were useful in defining alternate biomarker positive subgroups. The precision medicine interim analysis is now planned to be performed at the end of the study, due to sample size and feasibility concerns. The precision medicine aspect of the interim analysis now planned is to determine whether biomarker negative participants (using the pre-specified definition of biomarker positive and negative participants) should continue to be assigned to the intervention (see Section 7.7.1).

7.8 Precision Medicine Final Analysis

The monotonicity assumption that the treatment effect is increasing with the value of the primary biomarker will be tested by fitting a model with treatment and treatment by biomarker interaction. If the interaction term is significant at 0.1 level, we will conclude that the treatment effect is increasing or decreasing with the biomarker value depending on the sign of the estimated interaction. If this test yields results different from our initial assumption, the multiple cutoff analysis described in Section 7.4.1 will be repeated according to the adjusted assumption of monotonicity. We will explore a possibility that the treatment effect has a U-shape as a function of a biomarker and consider subgroups defined as the biomarker $\geq b_i$ and the biomarker $\leq b_j$ for $i < j$, $i = 1, \dots, 5$, $j = 1, \dots, 5$. These analyses will be repeated when the best subgroup is defined as the one maximizing the weighted average of the test statistics for the three outcomes with equal weights. These analyses are of an exploratory nature.

To evaluate the predictive effect of the biomarker, if such an effect is monotone, we will evaluate the correlation between the treatment effect and the biomarker. For each intervention with a continuous primary predictive biomarker, we will compute ρ_A , the correlation between the patient's response to active treatment and the patient's baseline (prior to period 1) biomarker value, and ρ_P , the correlation between the patient's response to placebo and the baseline biomarker. If the participant does not have a matching placebo, we will use response data on all (one or two) placebos on the participant. If there are two placebos, we will take the average. This analysis will be repeated using the biomarker value measured right before the corresponding treatment period.

The best subgroup for an intervention is defined as the subgroup that maximizes the power of detecting a treatment effect under the global null hypothesis relative to its alternative, namely, the null hypothesis that the intervention has no effect on the two primary endpoints, FEV₁ and ACQ-6, and the key secondary endpoint, CompEx, versus the alternative hypothesis that there is an effect on at least one of these endpoints. For a single outcome, this definition is equivalent to maximizing the square root of the size of the subgroup measured by its prevalence in the relevant patient population multiplied by the average treatment effect in the subgroup. This approach to defining the best subgroup reflects not only the treatment effect in the subgroup but also the size of the subgroup. Potential target subgroups with prevalence smaller than 16% will not be considered.

The primary predictive biomarkers are: blood eosinophils for imatinib, interleukin 6 for clazakizumab, genotypes rs7669660 and rs11547772 for cavosonstat, blood eosinophils for Broncho-Vaxom, and fractional exhaled nitric oxide (FeNO) for MCT. For each of the three outcomes, FEV₁ and ACQ-6 and CompEx, a model like the primary analysis model is fit that includes fixed effects for each biomarker, two-way interactions among the biomarkers, the biomarkers' interactions with treatment, and the biomarkers' two-way interactions with treatment. The one (1) standard deviation method¹⁰ and the overlapping group exponential Lasso penalty approach¹¹ with a penalty term that leads to more likely selection of subgroups defined by a smaller number of biomarkers will be used. Three models will be fitted, one for each outcome. From the fitted model for outcome Y_j , $j = 1, 2, 3$, a set of estimated linear predictors, $\hat{\eta}_1, \dots, \hat{\eta}_n$, is obtained for the set of biomarker vectors through plugging in estimated model coefficients. The target subgroup is then estimated based on a weighted average of three test statistics,

one for each outcome. The best subgroup is the subgroup that maximizes the power of the hypothesis test.

The resulting subgroup definition will be reported out as the best estimate of the types of patients who should be targeted by the intervention, satisfying the second primary study objective. These results can guide the design of further studies of the interventions found to have benefit in PrecISE. We will estimate the best subgroup for each intervention using primary predictive biomarkers. Then the analysis will be repeated with primary and available secondary predictive biomarkers. The secondary predictive biomarkers include: serum tryptase, sputum polymorphonuclear neutrophils (PMNs), sputum tryptase, and Urinary PGD-2-metabolite for imatinib; high sensitivity C-reactive protein (HS-CRP) for clazakizumab; change in maximal BD FEV₁ for cavosonstat; and urine bromotyrosine for assessment of TH2 inflammation, and assessment of T cell profile in circulation for MCT. The target subgroup will be estimated using the same methodology as specified above. The treatment effect in the estimated subgroup for each intervention will be tested using a 2-fold cross-validation with bootstrap methodology. This methodology preserves the Type I error probability of the testing procedure.

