For a given intervention and outcome let T_k^* be the test statistic for the treatment effect in biomarker positive participants and T_k^{All} be the test statistic in all participants computed using stage k , $k = 1, 2$, data. The tests are from the corresponding MMRM (subscripts indicating intervention and outcome are omitted here). In the final analysis, the treatment effect of a given intervention with respect to that outcome is performed using the inverse normal combination approach by computing the p-value: $p = 1 - \Phi(\sqrt{0.45} \Phi^{-1}(1 - p_1) + \sqrt{0.55} \Phi^{-1}(1 - p_2))$. Here p_1 and p_2 are the stage 1 and stage 2 p-values. The first stage p-value, p_1 , is computed based on the test statistic $\max(T_1^*, T_1^{All})$ using the skew normal distribution with parameters $(0, 1, .32)^6$ as a reference distribution. If the biomarker negative subgroup is not dropped at the interim analysis, the second stage p-value is computed similarly to the stage 1 p-value. If the biomarker negative subgroup is dropped at the interim analysis, the second stage p-value, p_2 , is computed based on the test statistic T_2^* using the standard normal distribution as a reference distribution. The weights $\sqrt{0.45}$ and $\sqrt{0.55}$ in the inverse normal formula correspond to a futility analysis performed at the 0.45 information fraction. If futility is performed at an information fraction xt , the weights \sqrt{x} and $\sqrt{1-x}$ will be used. For interventions without an interim analysis, the final analysis for a given outcome is performed as follows. Five possible cutoffs b_1, b_2, b_3, b_4, b_5 are identified for the primary continuous biomarker that defines the biomarker positive subgroup for that intervention. The five potential subgroups are defined as participants with the biomarker values $\geq b_i$ if the treatment effect is assumed to be increasing with the biomarker values, and $\leq b_i$ otherwise. The test statistic $\max(T^1, T^2, T^3, T^4, T^5, T^{All})$ is compared with 2.163 for a 0.05 one-sided level and with 2.452 for a 0.025 one-sided

level. These critical values were computed based on the joint distribution of the six test statistics under the null hypothesis and assuming that the cutoffs represent the quantiles of the biomarker distribution.⁷

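### SAP 7.8 sets out to explore a U-shaped treatment effect, but the subgroups it defines are middle intervals of the biomarker, which suit an inverted U

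*SAP*

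**What the plan says.** SAP 7.4.1 covers the final analysis of interventions that have no interim analysis. Five cut-offs, b_1 to b_5, "are identified for the primary continuous biomarker that defines the biomarker positive subgroup for that intervention". Each gives a one-sided subgroup: at or above the cut-off if the effect is assumed to increase with the biomarker, at or below it otherwise. The largest of the five subgroup statistics and the all-participant statistic "is compared with 2.163 for a 0.05 one-sided level and with 2.452 for a 0.025 one-sided" level, "assuming that the cutoffs represent the quantiles of the biomarker distribution".

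SAP 7.8 first tests the assumed direction with a treatment-by-biomarker interaction and repeats the cut-off analysis if the direction changes. It then says it will explore whether benefit "has a U-shape as a function of a biomarker and consider subgroups defined as the biomarker $\geq b_i$ and the biomarker $\leq b_j$ for" index pairs in which the first is below the second, both running from 1 to 5. It labels these analyses exploratory.

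Later in 7.8 the best subgroup for a single outcome is the one that maximises the square root of prevalence times mean effect, with a 16% floor on prevalence. A penalised model then follows, and after it the statement: "The resulting subgroup definition will be reported out as the best estimate of the types of patients who should be targeted by the intervention".

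**The concern.** A treatment effect that is U-shaped in the biomarker is large at low and high values and small in between. The subgroup that matches it is the two tails taken together. The sentence in SAP 7.8 instead joins a lower bound b_i to an upper bound b_j with i < j. On the ordinary reading that is the stretch between two cut-offs, where a U with a central minimum gives least.

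Optimising the target subgroup is the trial's second primary objective, and this is the only sentence in 7.8 aimed at a U-shaped effect. A programmer cannot follow both its label and its rule. If the mismatch is settled only after results are seen, the choice of shape becomes post hoc.

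**Working it through.** **Inputs.** Five cut-offs and the critical values come from SAP 7.4.1. The interval rule, the scoring criterion and the 16% floor come from 7.8. The 0.3 SD effect, correlation 0.70 and n = 93 come from SAP section 5. The direction comes from 7.7.1, where larger statistics are more favourable. Assumptions made here: ascending cut-offs and the effect shapes, each scaled to an overall mean of 0.30 SD.

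**1. Where the cut-offs lie.** The SAP says quantiles but not which. For nested subgroups with prevalences 1/6, 2/6, ..., 1, two statistics correlate as √(smaller prevalence / larger prevalence). Simulating the maximum of the six (4 million draws) gives critical values 2.162 and 2.451, against the SAP's 2.163 and 2.452. The tail probabilities beyond the SAP's values are 0.0499 and 0.0249. Sextiles therefore reproduce the plan's figures, and they are used below.

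**2. What the rule selects.** The result depends on the cut-off order and on how the joining word is read:

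| Cut-offs | Both conditions hold | Either condition holds |
|---|---|---|
| Ascending | middle interval b_i to b_j | everyone |
| Descending | nobody | two tails |

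With ascending cut-offs there are ten intervals, and none reaches below b_1 or above b_5. This follows from the definition alone. The tails appear only if the order is descending and the two groups are pooled. The text states neither.

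**3. Quadratic U by hand.** Let u be the biomarker's percentile rank (0 to 1) and the effect 0.9(2u − 1)², whose overall mean is 0.9 × 1/3 = 0.30 SD.
- Widest interval, b_1 to b_5: |2u − 1| ≤ 2/3, so the mean is 0.9 × (2/3)²/3 = 0.133 SD. Prevalence is 2/3 and the score is √(2/3) × 0.133 = 0.109, the best of the ten.
- All participants: 1 × 0.30 = 0.300.
- Two outer sixths: mean (0.30 − 2/3 × 0.133)/(1/3) = 0.633 SD, score √(1/3) × 0.633 = 0.366.
- One outer sixth: √(1/6) × 0.633 = 0.259.

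All ten written intervals have a mean effect below 0.30 SD (0.03 to 0.23). All ten two-tail sets have a mean above it (0.31 to 0.63).

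**4. Other shapes, best score in each class.**

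| Effect shape (overall 0.30 SD) | Written interval | All participants | One-sided | Two tails |
|---|---|---|---|---|
| Quadratic U | 0.109 | 0.300 | 0.259 | 0.366 |
| V | 0.163 | 0.300 | 0.237 | 0.327 |
| 0.45 SD in outer thirds only | 0.184 | 0.300 | 0.260 | 0.367 |
| 0.9 SD in outer sixths only | 0 | 0.300 | 0.367 | 0.520 |
| Off-centre U, minimum at 35th percentile | 0.188 | 0.300 | 0.397 | 0.374 |
| Inverted U | 0.313 | 0.300 | 0.304 | 0.268 |

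For the two step shapes: 0.45 × √(1/6) = 0.184, 0.45 × √(1/3) = 0.260 and 0.45 × √(2/3) = 0.367; 0.9 × √(1/6) = 0.367 and 0.9 × √(1/3) = 0.520.

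**5. Selection in samples.** With n = 93, correlation 0.70 and 20,000 runs under the quadratic U, the best written interval beats the all-participant statistic in 3.0% of runs. When two-tail sets are added, one of them is chosen in 99.0%. Under the inverted U, a written interval beats the all-participant statistic in 69.7%.

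**The case against.** The strongest case is that this is loose wording with little consequence. Much of it stands.

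- **Order of the cut-offs.** It is never stated. With descending labels and the two conditions read as pooled groups, the sentence gives exactly the two tails. A reader might therefore infer too much in saying that the rule cannot find a U under any reading. The two-tail reading, however, needs two assumptions that the text does not make.
- **The label may be the error.** If an inverted U was meant, the intervals are right. CompEx, one of the three outcomes in 7.8, is summarised in SAP Table 2 as a ratio with values below 1 favourable. On that scale a U does put the benefit in the middle. This leaves the intention open, but the sentence is still inconsistent for FEV₁ and ACQ-6, where 7.7.1 makes larger statistics favourable.
- **Steering towards those who benefit least.** A reader might infer that the search would recommend the middle patients. The figures do not support that. If the all-participant statistic stays in the comparison, as it does in 7.4.1, it usually wins. The likely failure is a missed subgroup.
- **One-sided subgroups.** They can catch one tail. They beat no selection when the effect sits in the outer sixths (0.367 against 0.300). They even beat the two-tail sets for the off-centre U (0.397 against 0.374), provided the assumed direction is the right one. For that shape 2 of the 10 written intervals also exceed the overall mean effect.
- **The second primary objective.** A reader might infer that the reported target subgroup is compromised. The statement about reporting it follows the penalised model, and nothing shows that a U-shape interval feeds into it. That model lists no quadratic biomarker term, so it does not clearly fill the gap either.
- **Plausibility.** No document gives evidence that any intervention has a U-shaped effect.

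**Conclusion.** The point holds as a contradiction between the label and the rule in one sentence of SAP 7.8. Given ascending cut-offs, the exclusion of both ends is certain. The size of the loss (0.11 against 0.30 and 0.37) is illustrative: it rests on sextile cut-offs and a quadratic U with a central minimum. In all five non-inverted shapes tried, the best written interval scored below no selection at all, so the search would usually miss a two-tail subgroup.

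The reach is limited. The search is exploratory and needs a continuous primary biomarker, so cavosonstat, which is defined by genotype, falls outside it. The primary tests and the 2.163 and 2.452 critical values are untouched, and no effect on the model-based subgroup is shown. The correction is worth making because it is cheap and fixes the choice of shape in advance.

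**What to change.** In SAP 7.8, before unblinding for the analyses concerned:

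1. State that b_1 < b_2 < b_3 < b_4 < b_5.
2. Define the U-shape candidates as biomarker ≤ b_i or biomarker ≥ b_j, with i < j.
3. Keep the existing intervals and relabel them as inverted-U candidates.
4. For both sets, keep the all-participant comparator, the 16% minimum prevalence and the exploratory label.

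This covers both shapes, whichever was meant. The cost is a short rewording and up to ten more candidates (five cut-offs taken two at a time), which makes the exploratory search somewhat larger. SAP 1.4 restricts edits to the blinded statisticians once an intervention has had an unblinded review, so they should make the change.

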1.3 Other Study Design Changes

We performed a planned blinded interim analysis of the within-subject (between-period) correlation (not adjusted for treatment) for the PrecISE crossover trial design. The analysis was performed on 64 pairs of observations from consecutive crossover periods. The estimated within-subject correlation for the CompEx² endpoint was 0.33, lower than the value of 0.38 assumed for the power analysis and sample size determination specified in the protocol. This is due, in part, to a lower-than-expected CompEx event rate. The estimated within-subject correlation for the other two primary endpoints, FEV₁ and ACQ-6, was 0.7 or higher. Based on this information and external data on within-subject correlation

for FEV₁ and ACQ, 0.7 was used as the within-subject correlation for re-calculating the required sample size.

CompEx is a novel endpoint which combines exacerbations and deterioration events that are not exacerbations. It relies on study participants to record their peak flow, symptoms and rescue use twice daily. Participant compliance with their daily diaries was lower than expected. This information plus the low correlation and its impact on the power available to detect an intervention effect with respect to CompEx contributed to the decision to remove CompEx as a primary endpoint in the study and consider it a key secondary endpoint.

The target sample size of the study has been revised to 395 participants, due to the change from three to two primary endpoints and change in crossover correlation assumptions for the efficacy analysis. The enrollment period has been extended to a duration of 42 months, compared to the originally planned 30 months. The study period has been extended to a duration of 54 months, with the last patient visit expected in December 2024 and safety follow-up expected to conclude in February 2025. The revised study period and sample size should be sufficient to support our investigation of the five interventions currently active in the PrecISE master protocol. We estimate a total of 1000 treatment periods will be available to contribute to the statistical analyses for evaluation of efficacy and optimization of target subgroups for each intervention. With the current study timelines and enrollment goals, each participant should be able to complete a minimum of two treatment periods and a maximum of six, including at least one placebo period, depending on their time of enrollment.

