An intervention is considered efficacious if significant benefit is shown for either of the two primary endpoints (FEV₁, or asthma symptom control score). Because there are multiple chances for an intervention to demonstrate efficacy, multiplicity adjustments are required. We will use the Hochberg method to adjust for multiplicity. According to the Hochberg method, the treatment is declared effective if the treatment-placebo comparison is significant at level α for both outcomes or it is significant at $\alpha/2$ for at least one of the outcomes.

A sample size of 111 participants for each intervention is required to achieve at least 80% power to detect a treatment effect with respect to at least one of the two primary endpoints equal to 0.3 times the standard deviation (SD) of that outcome, taking into account the possibility of stopping for futility with a non-binding stopping rule. If participant accrual in the target subgroup of one or more interventions is such that an interim futility analysis is not possible or practical (e.g., the study will conclude before the recommendations of the interim futility analysis can be implemented), the interim analysis will not be performed. In this case, 93 participants (2:1 ratio of biomarker positive to negative participants) are required to provide similar power for the final analysis.

All participants randomized to an active intervention or matching placebo will be included in the final efficacy analysis, but only participants who do not withdraw from the study prior to the start of period 2 are counted towards the required total sample size in estimating power. We also assume that about 10% of participants will discontinue an active treatment period soon after randomization in the power calculations. Attrition is monitored throughout the study, and the required sample size may be adjusted, if the treatment discontinuation rate is different from 10% or discontinuations occur later in the treatment period. This adjustment, if needed, will take place prior to any unmasking of treatment assignments, that is, prior to the interim futility analysis or, if the futility analysis is not feasible for an intervention, prior to the final analysis.

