7.3 Unblinding for Interim and Final Analyses of Each Intervention

Both interim and final analyses for each intervention are conducted independently of other interventions, consistent with the master protocol design. Statistical analyses for Intervention A are based on participants randomized to Intervention A during the trial. The treatment periods in which participants were randomized to A plus matched placebo periods contribute to the analysis. For participants without a matched placebo, all placebo periods will be included in the analysis. For analyses based on the mITT and per protocol populations, the treatment periods included in the analyses are limited to those satisfying the respective mITT and per protocol criteria stated above. Other treatment periods from the participant might be used in the analysis to estimate the within-participant correlation in the crossover if the primary model does not converge.

The target sample size for the interim analysis of Intervention A, with objective to test for futility, is 34 biomarker positive participants and 17 biomarker negative participants.

Once an intervention achieves the target sample size for an interim analysis, an appropriate data cut-off is determined for the interim analysis (sufficient to allow completion of data acquisition for the treatment periods contributing to the analysis), analysis files are generated, and analyses conducted by the independent unblinded project statistician for submission to the DSMB.

Upon achievement of the final target sample size for an intervention (111 participants), randomization to that intervention stops. Because interventions may stop at different times in the study, and placebo period data are shared across interventions, care will be taken to observe firewalls that protect confidentiality of data and analysis results for one intervention while other interventions continue to accrue participants. If, for example, data for Intervention A are reported publicly, while the study continues (e.g., A was stopped early for futility), then information about placebo periods included in the

report for A will be limited to comparative group analysis results only. No rare events or within-group event rates that could potentially unblind treatments in the ongoing trial or motivate conjecture about the results of the ongoing interventions will be reported.

Study close-out procedures will not be implemented until all interventions are completed.

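### SAP 7.8 sets out to correlate the treatment effect with the biomarker, but computes separate active and placebo correlations that do not determine it

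*SAP*

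**What the plan says.** The second paragraph of SAP 7.8 takes up the predictive effect of the biomarker, on condition that the effect is monotone. Its stated aim is: "we will evaluate the correlation between the treatment effect and the biomarker". Two quantities follow. ρ_A is "the correlation between the patient's response to active treatment and the patient's baseline (prior to period 1) biomarker value". ρ_P is "the correlation between the patient's response to placebo and the baseline biomarker".

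A participant without a matching placebo contributes whatever placebo data exist: "If there are two placebos, we will take the average". The paragraph ends: "This analysis will be repeated using the biomarker value measured right before the corresponding treatment period".

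The SAP gives no formula combining ρ_A and ρ_P, no test or interval for their difference, and no rule for reading that difference. The step covers continuous biomarkers only, so cavosonstat, which is targeted by genotype, falls outside it.

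The paragraph before it fits a treatment-by-biomarker interaction, judged at the 0.1 level, to settle the direction of monotonicity. The remark that the work is exploratory closes that earlier paragraph and is not repeated for the correlations.

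**The concern.** The stated target is a correlation with an effect, that is, with a difference between active and placebo. The stated calculation yields two correlations with single-treatment responses. Each is scaled by the SD of its own treatment's responses, so a gap between them mixes effect modification with any difference in variability. The crossover supplies the needed quantity directly, as each participant's own active-minus-placebo difference, and this step does not use it.

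Refining the target subgroups is a primary objective. A reader given ρ_A and ρ_P under this description will naturally take a gap as evidence of prediction and no gap as evidence against it. Either inference can be wrong. The figures could also disagree with the interaction test in the same section, and the SAP has no rule for resolving that.

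**Working it through.** The plan states no numerical result for this step, so there is no figure to reproduce.

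**Inputs from the documents**
- Between-period correlation τ = 0.70 (SAP 1.3: "0.7 was used as the within-subject correlation for re-calculating the required sample size").
- Sample size per intervention: 111 (SAP 7.3: "Upon achievement of the final target sample size for an intervention (111 participants), randomization to that intervention stops"), or without an interim analysis (SAP section 5): "93 participants (2:1 ratio of biomarker positive to negative participants) are required to provide similar power for the final analysis".
- About 25% of participants are expected to have two placebos (SAP 1.1).

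**Assumed, because the documents do not give them**
- Active-to-placebo SD ratio: 0.8 to 1.3, plus one deliberately extreme case.
- Correlation of placebo response with the biomarker: 0.3 to 0.5.

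**1. What the target needs.** Let D be active minus placebo, B the biomarker, and s_A and s_P the response SDs. Then

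corr(D, B) = (ρ_A s_A − ρ_P s_P) / √(s_A² + s_P² − 2τ s_A s_P).

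The two planned correlations supply two of five inputs. With equal SDs and τ = 0.70 this reduces to (ρ_A − ρ_P)/√0.6 = 1.29(ρ_A − ρ_P), so 0.3 and 0.1 give 0.26. With unequal SDs, equal correlations do not mean zero. At ρ_A = ρ_P = 0.3:
- SD ratio 1.2: (0.36 − 0.30)/√(1.44 + 1 − 1.68) = 0.06/0.872 = +0.07.
- SD ratio 0.8: (0.24 − 0.30)/√(0.64 + 1 − 1.12) = −0.06/0.721 = −0.08.

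**2. A biomarker that predicts nothing.** No linear interaction means ρ_A s_A = ρ_P s_P, so ρ_A = ρ_P (s_P/s_A).

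| SD ratio, active/placebo | ρ_A if ρ_P = 0.30 | ρ_A if ρ_P = 0.50 |
|---|---|---|
| 0.8 | 0.38 | 0.63 |
| 1.0 | 0.30 | 0.50 |
| 1.2 | 0.25 | 0.42 |
| 1.3 | 0.23 | 0.38 |

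With equal SDs and no averaging of placebos, the two population values agree exactly when there is no linear interaction. The problem therefore needs unequal SDs and a non-zero prognostic correlation.

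**3. A true interaction that is hidden.** Give placebo responses total variance 1 and residual variance 0.3. Double the residual SD on active, set the prognostic slope at 0.30 and add an interaction of 0.12 SD per biomarker SD. The active variance is 0.42² + (0.70 − 0.09) + 4 × 0.30 = 1.986, with SD 1.409. Then ρ_A = 0.42/1.409 = 0.30, the same as ρ_P. Meanwhile corr(D, B) = 0.12/√(0.0144 + 0.30 + 1.20) = 0.10. In simulation at n = 93 a dependent-correlations test rejects about 10% of the time at nominal two-sided 10%, so it has no power. The test on the paired difference rejects about 25%.

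**4. Placebo averaging.** The mean of two placebos has SD √((1 + 0.70)/2) = 0.92. If 25% of participants were averaged, ρ_P would rise by the factor 1/√(0.75 + 0.25 × 0.85) = 1.02, from 0.300 to about 0.305. This is negligible.

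**5. Power and false signals** (simulation; n = 93, τ = 0.70, prognostic correlation 0.30, two-sided 0.10, 25% of placebos averaged)

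| Setting | Dependent-correlations test on ρ_A, ρ_P | Paired difference |
|---|---|---|
| Interaction 0.15 SD, equal single-period SDs | 0.52 | 0.60 |
| Interaction 0.20 SD, equal single-period SDs | 0.72 | 0.80 to 0.81 |
| No interaction, active residual SD × 1.25 | 0.12 | 0.10 |
| No interaction, active residual SD × 2 | 0.23 | 0.10 |

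Without averaging, the first two rows become 0.52 against 0.58 and 0.73 against 0.78. In the last row ρ_A averages 0.22 and ρ_P about 0.30, while corr(D, B) averages 0.00. Doubling the residual SD corresponds to a total SD ratio of √(0.70 + 4 × 0.30) = 1.38, beyond the assumed range.

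**The case against.** The strongest reply is that little in the plan rests on these two numbers. SAP 7.8 tests effect modification directly through the treatment-by-biomarker interaction. It then estimates the best subgroup from interaction models built like the primary model, and it is that subgroup definition which the SAP says satisfies the second objective. The primary model in SAP 7.4.1 has a subject-level random intercept, so the pairing is naturally used there, although 7.8 does not say so for its interaction test. SAP 3.1 attaches no formal hypothesis to the objective, and no decision depends on ρ_A or ρ_P. All of this stands. A reader might infer that the plan's main evaluation of predictive biomarkers is unsound; the documents do not support that.

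A reader might also infer a very large loss of power. If the two correlations were compared as though they came from separate samples, detection at n = 93 would be about 10% against 60% for a 0.15 SD interaction, and 25% against 81% for 0.20 SD. But the SAP specifies no such comparison, and it would be invalid for correlations from the same people, rejecting under 1% of the time at nominal 10% when SDs are equal. Those figures are not a property of the plan.

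Nor is placebo averaging a material source of bias. It applies only where there is no matching placebo, and step 4 shows a trivial shift even at 25%.

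What the reply does not remove is the mismatch itself. A dependent-correlations test, which the SAP does not specify either, restores most of the power under equal SDs but does not cure the unequal-SD problem.

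**Conclusion.** The point holds as a mismatch between a stated target and a stated calculation. ρ_A and ρ_P are not the correlation with the treatment effect, do not use the pairing, and cannot be converted into the target without both SDs and the between-period correlation. That much is algebra and needs no assumption.

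The size is modest. Against a valid comparison the power loss at n = 93 with equal single-period SDs is about 5 points without averaging and 8 to 9 points if 25% of placebos are averaged. The risk of a false signal depends on SDs by treatment, for which the documents give nothing: about 12% at nominal 10% if the active residual SD is 1.25 times the placebo value, and 23% in the illustrative case where it is doubled. All these figures assume a prognostic correlation of 0.30.

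The consequence is confined to this correlation summary. It is worth correcting because the figures are offered as a measure of prediction under a primary objective, and the correction is cheap.

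**What to change.** In SAP 7.8, make the reported measure the correlation, with a confidence interval, between each participant's active-minus-placebo difference and the baseline biomarker. Use the matched placebo where there is one, otherwise the mean of the available placebos. Present it beside the treatment-by-biomarker interaction estimate from the paired mixed model, and say explicitly that this model accounts for the pairing. Retain ρ_A and ρ_P as descriptive figures only.

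The repeat with proximal biomarkers needs one more sentence. A difference spans two periods, each with its own biomarker value, so the SAP should state which is used, for example the value before the active period.

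The cost is a short edit using data already collected. Participants lacking either an active or a placebo value drop out of this one summary; no other analysis changes.
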